### 3.3 Exclusion Criteria

1. Symptomatic patient ECOG  $\geq 1$
2. Poor liver function, Child-Pugh  $\geq B8$ .
3. Ascites or encephalopathy
4. Extrahepatic tumor disease
5. Tumor invasion of the main portal vein
6. Serum bilirubin  $> 3 \text{ mg / dL}$
7. Cre clearance  $\leq 60 \text{ mL / min}$
8. Patients in whom the following elements are contraindicated or present:
  - a. Doxorubicin use

- b. Documented allergy to iodinated contrast
- c. CT and MRI scans
- d. Liver embolization procedures
- e. White blood cell count <2000 cells / mm^3
- f. Neutrophils count <1500 cells / mm^3
- g. Cardiac ejection fraction < 50 percent
- h. Platelet count <5 x 10^4 / mm^3, PT-INR > 2.0)
- i. AST and / or ALT > 5x or when they exceed > 250 u / l
- j. Known Hepatofugal blood flow
- k. Gross intrahepatic A-V fistula

- 9. Pregnant or lactating women.
- 10. Tumor load greater than 50% of liver volume.
- 11. Active fungal or bacterial infection.
- 12. Other concomitant tumors.
- 13. Any comorbidity, condition or event that, in the opinion of the investigator, puts the patient at an undue risk that discards the use of DEB-TACE.
- 14. Patients who do not wish to participate and / or who refuse to give their written consent

### **3.4 Expected number of participants and justification**

It is an observational and descriptive study. As far as we know, no data have been published in the literature on the proportion of adverse effects / complications associated with the administration of QETA with 100 micron microspheres, so it has not been possible to make a sample size predetermination based on data previous. It is intended to include 10 patients per center, which would make a total of 130 patients. With this sample size, an accuracy of 1.71% can be achieved in the estimation of a proportion through a bilateral asymptotic confidence interval of 95.00%, assuming that the proportion of the event is 1.00%.

## **4 STUDY DEVELOPMENT**

### **4.1 Description of the technique**

TANDEM™ 100 µm microspheres, accurately calibrated, should fill the vasculature of the tumors when they are administered by placing the super-selective microcatheter, relocating it according to the needs and thus allowing a selective embolization on the hepatic segmental arteries of each tumor nodule.

The chemoembolization procedure is carried out under strict aseptic conditions, under conscious sedation or general anesthesia, with antibiotic prophylaxis, IV analgesia and antiemetic medication. Before chemoembolization, an angiography of the hepatic and mesenteric arteries is performed to assess the vascular anatomy of the liver, check for arteriovenous fistulas and identify the nutritional arteries of the tumor.

Chemoembolization is carried out by selective catheterization of hepatic segmental arteries with insertion into the lesion or lesions of a coaxial microcatheter. The tip of the microcatheter is located in the vessel or vessels that supply the tumor and at the same time it is checked that sufficient flow reaches the tumor (fluoroscopic verification with contrast agent). The

microcatheter should not be forced to avoid occluding or spasmodizing the nutrient artery of the tumor.

The TANDEM-DOX chemoembolization protocol (100  $\mu$ m) consists of the superselective injection of a maximum of 3 ml of microspheres loaded with 50 mg / ml of doxorubicin. It will be mixed with 5-10 ml of non-ionic iodinated contrast before administration. The microspheres will be slowly injected into the vessels that water the tumors at a rate of approximately 1 ml / min. It is essential that the injection be slow to obtain the best results. The microspheres should be injected under strict real-time control with high resolution fluoroscopy.

When the flow begins to reduce, you should stop, wait a few minutes before restarting the injection. In general, the flow will increase again and an additional volume of microspheres may be administered when the microvasculature relaxes after the initial blockage. The goal is to saturate as much of the tumor bed as possible. Transarterial chemoembolization is considered a technical success when the previously established dose of drug has been administered or when the complete stasis of tumor arterial vascularization is reached. If after administering the desired dose of drug / embolization, blood flow is still detected in the tumor, no other embolizing agent or particle will be administered.

#### **4.2 Follow-up**

After the first TACE procedure, the following evaluations will be carried out:

1. Clinical and analytical control 10-20 days after discharge according to usual practice: Clinical visit in which the general condition of the patient is assessed and will be asked whether or not he had Sd. Post-pay, its duration and intensity. Analytical including blood count, coagulation tests, basic biochemistry, transaminases and bilirubin. The study may be extended with more complete imaging or analytical tests if the physician considers it necessary.
2. Dynamic liver CT or MRI every 3 m for the first 6 months and then twice a year according to usual practice.
3. Clinical and laboratory review every 3 m the first 6 months and then twice a year as usual practice until the progression, death or loss of patient follow-up, with a maximum of 5 years.
  - a. Quality of life assessment (ECOG)
  - b. Laboratory assessment
  - c. Evaluation of safety and efficacy and assessment of retreatment if appropriate.

### **5 TUMOR RESPONSE ASSESSMENT**

#### **5.1 Study Variables**

Related to the patient and the disease: age, gender, etiology of liver disease, diagnosis of HCC, previous nodules treated with surgery, ablation or TACE, Child-Pugh score, BCLC stage of the tumor, size, location and number of patients. nodules, segmental vascular

invasion of the portal vein, bilioenteric shunt or previous biliary prosthesis, carrier of porto-systemic shunt, relevant concomitant pathologies.

- Variables related to the primary objective:

**Post-embolization syndrome:** in an adverse effect of TACE that is defined as a picture of abdominal pain, fever  $<38.5^{\circ}\text{C}$ , and variable degree leukocytosis that appears 24 hours after the procedure and can last up to 10 days. It can be accompanied by nausea, vomiting and asthenia. It is related to tissue necrosis and is self-limited, its treatment is symptomatic. Its incidence is variable and linked to the volume of necrotic tissue.

**Early adverse events** derived from the procedure during the first 30 days:

1. Liver failure defined by ascitic decompensation with elevation of serum Br, jaundice and transaminases  $>x5$  and / or hepatic encephalopathy.
2. UGIB of peptic or varicose origin
3. Intense pain that requires continued iv medication
4. High fever that is not justified by Sd. post refund
5. Liver abscess
6. Coagulative portal thrombosis
7. Acute pancreatitis
8. Acute cholecystitis
9. Renal failure, elevation of serum Cr  $\times 2$  its baseline value.
10. Pleural effusion

**Late adverse events** arising from the procedure between the first 30 days and 6 months:

1. Intrahepatic bile duct injury defined by dilation of biliary radicals with cholestatic symptoms.

Additional therapies against cancer (sorafenib, radioembolisation, symptomatic treatment) will be documented for all patients every three months until death.

**Mortality** in the first 30 days after treatment

- Variables related to secondary objectives: the information will be obtained from imaging studies performed interchangeably with liver MR or CT using intravenous contrast and performing three-phase dynamic studies (arterial, portal and balance phase). Imaging studies will be evaluated according to RECIST 1.1 criteria.
  - **Tumor response.** Devascularization pattern according to RECIST 1.1 criteria. Response to treatment: The response will be classified as objective response, (OR) complete (CR), partial (RP), stable disease (EE) and tumor progression (PT) (2, 31, 32)
  - **Overall Survival (OS)**
  - **Cause of Death:** Tumor progression, complications of liver disease or others.

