## BACKGROUND AND JUSTIFICATION OF THE STUDY

According to the guidelines of the European Association for the Study of the Liver (EASL) and the American Association for the Study of Liver Diseases (AASLD), radiofrequency, surgery and liver transplantation are considered radical curative treatment modalities for HCC in early stage as long as they are anatomically / clinically feasible (1,3-5).

Transarterial chemoembolization (TACE) is the formal indication for the treatment of intermediate stage HCC. This treatment has a level of evidence 1 A increasing the overall survival of these patients. TACE is performed using ultraselective catheterization techniques, under high quality fluoroscopic guidance, using microcatheters. The intrahepatic artery or arteries that nourish the HCC are channeled as selectively as possible to release the therapeutic agent there (6-8).

There are considerable variations in the embolization-chemoembolization technique in relation to the choice of materials, aspects of the procedure, drug and dose used, "end point", number of sessions and space between them etc etc ... (9). There are basically two ways to apply the TACE. Conventional TACE (c-TACE), initially described in 1983, is in which lipiodol is emulsified with doxorubicin and acts as a cytostatic vehicle (10). In the past decade, synthetic microspheres have been developed that can be preloaded with doxorubicin or irinotecan drug eluting beads giving rise to TACE with microspheres (deb-TACE). This has the advantage of increasing the dose and exposure time between the neoplastic cells and the tumor while practically nullifying the systemic effect of doxorubicin. The appearance of the synthetic microspheres that are both vehicle and drug-releasing has decreased the toxicity of the treatment and has also decreased its variability (11). However, there are still many unknowns regarding the ideal TACE.

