## 1.2 Route of activation and mechanism of action

Embozene TANDEM™ microspheres have been designed to ionically absorb and bind positively charged molecules. The antineoplastic agent doxorubicin hydrochloride is an effective positive loading drug for the treatment of HCC. This drug, when administered systemically (intravenously), has an important toxic profile that normally limits its use. After their local and selective administration in the tumor through an intra-arterial microcatheter, the microspheres release the drug (doxorubicin) in the embolic zone by diffusion. The release of the drug depends on its physical properties, the concentration of local ions and the local pH. The released doxorubicin is then dispersed through the surrounding tissue and interacts with the metabolizing cells to inhibit duplication and ultimately kill the affected cells.

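### Section 5.1 defines no blood-count toxicity for a doxorubicin-loaded product, although a blood count is already scheduled, so the rate of low counts will be unevenly ascertained and lack a clear denominator

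*Combined protocol and SAP*

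**What the plan says.** The primary objective (Section 1.1, Primary Objective) is the tolerance and safety of the doxorubicin-preloaded microspheres. It covers post-embolization syndrome, major and minor adverse events to day 30, and treatment-related mortality.

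Section 5.1 gives the variables for that objective. It names ten early events "derived from the procedure during the first 30 days": liver failure, upper gastrointestinal bleeding, intense pain, high fever, liver abscess, portal thrombosis, pancreatitis, cholecystitis, renal failure and pleural effusion. It names one late event, bile duct injury. The only blood-count item is part of post-embolization syndrome, and it is a rise: "variable degree leukocytosis that appears 24 hours after the procedure and can last up to 10 days".

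Section 1.2 (Route of activation and mechanism of action) says that doxorubicin given intravenously "has an important toxic profile that normally limits its use". Exclusion 8 in Section 3.3 places white cell, neutrophil and platelet limits beside contraindication to doxorubicin, for example "Neutrophils count <1500 cells".

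Section 4.2 schedules a control 10-20 days after discharge, following the first TACE. Its laboratory content is stated: "Analytical including blood count, coagulation tests, basic biochemistry, transaminases and bilirubin". Section 6.1 plans a descriptive analysis of the study variables and does not mention laboratory grades or change from baseline.

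**The concern.** This is a safety study of a drug-carrying embolic. The early events describe the embolic and procedural side in detail, with laboratory thresholds for liver and kidney. Blood counts, measured at the same early control, have no variable, no threshold and no analysis.

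A low count can still enter the data as an adverse event, but nothing says when it qualifies. Two centres seeing the same value could record it differently. The final report would then give a number of recorded cytopenias without saying how many patients had a count from which one could have been found. A low rate would partly reflect how low counts were handled, and a reader could not separate that from a low true rate.

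**Working it through.** **1. Laboratory measurements set against the variables that use them.**

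| Measured at the early control (Section 4.2) | Threshold in Section 5.1 |
|---|---|
| Transaminases | Above a five-fold limit, within the definition of liver failure |
| Bilirubin | Elevation, within liver failure |
| Basic biochemistry (presumably including creatinine) | Creatinine twice baseline, renal failure |
| Blood count | None for a fall in any cell line |

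Listed events defined by a low count: 0 of 10 early and 0 of 1 late.

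**2. Whether the count serves the leukocytosis item.** Leukocytosis is described as lasting up to 10 days. The control is at least 10 days after discharge, so at least 10 days after the procedure. The count therefore falls at or beyond the end of that window and contributes little to the one blood-count item that Section 5.1 contains.

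**3. The route left for a low count.** Section 7.1 says that an abnormal laboratory finding may be an adverse event. Section 7.2 requires the investigator to document all adverse events. Section 7.3 cites CTCAE 4.03 but then assigns maximum intensity to Minor or Major, defined by tolerability and by seriousness. An asymptomatic low count is Minor unless someone judges it medically important. No laboratory grade reaches a planned table.

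**4. Baseline.** Section 3.2 requires white cell, neutrophil and platelet results within two weeks of registration, so a baseline exists. Entry allows platelets just above 5 x 10^4/mm3, so a low later value may be pre-existing. Only a comparison with baseline separates the two, and none is planned. The entry limits also conflict: neutrophils above 1000 in Section 3.2 against exclusion below 1500 in Section 3.3, and white cells below 3000 excluded in the Summary against below 2000 in Section 3.3. These passages must be reconciled. The point made here does not depend on how.

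**5. Precision.** The plan's own figure reproduces. The asymptotic half-width is 1.96 x sqrt(p(1-p)/n); with p = 0.01 and n = 130 it is 1.96 x sqrt(0.01 x 0.99/130) = 1.71%, as in Section 6.2. At these frequencies the asymptotic interval is poor. The lower limit is 1.00 - 1.71 = -0.71%, and with no events the width is zero. An exact interval is needed.

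With no cases among m patients assessed, the exact two-sided 95% upper limit is 1 - 0.025^(1/m):

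- m = 130: 2.8%
- m = 104 (80% of 130 with a count): 3.5%
- m = 65 (50% with a count): 5.5%

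The 80% and 50% shares are assumptions. The documents do not say how many patients will have a count.

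**6. Uneven ascertainment.** If the true rate is t and a share s of cases is recorded, the chance of recording at least one case in 130 is 1 - (1 - ts)^130.

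| True rate t | s = 100% | s = 50% | s = 25% |
|---|---|---|---|
| 1% (the proportion assumed in Section 6.2) | 73% | 48% | 28% |
| 3% (assumption) | 98% | 86% | 62% |

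The values of s are assumptions that show the direction and range of the effect. They do not estimate it.

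**7. Timing.** If discharge is on day d, the control falls between days d + 10 and d + 20. The late end passes day 30 when d exceeds 10. The next review in Section 4.2 is at about three months. The Summary lists a 1-month visit, and the plan does not say whether this is the same control.

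**The case against.** The strongest reply is that the Section 5.1 list does not bound the endpoint. The primary objective covers all major and minor events to day 30. Section 7.2 makes recording mandatory and names direct questioning as a source, and Section 7.1 admits laboratory findings. This stands. A reader might infer that drug toxicity is left to voluntary reporting; the documents do not support that. What is missing is a prespecified rule, not a duty to record.

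A reader might also infer that the study fails to test the Background's statement about "practically nullifying the systemic effect of doxorubicin". That statement concerns drug-eluting beads as a class. No objective sets out to test it, and there is no comparator. Adding cytopenias would describe their frequency but could not establish reduced systemic toxicity.

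Cardiac toxicity is a third tempting extension, since Section 3.3 excludes "Cardiac ejection fraction < 50 percent". But a cardiac event that is life-threatening or leads to hospitalisation is already Major under Section 7.3, so an undefined cardiac item would add little.

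Two practical objections also have force. One early count after the first procedure may miss a nadir and does not cover retreatments, so it cannot by itself give a true worst grade. And Section 9.1 refers to a data collection booklet in an annex that is not in the text available here; it may already hold laboratory fields. That would make the change cheaper, but Sections 5.1 and 6.1 would still define no variable or analysis for the counts.

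**Conclusion.** The point holds as a refinement of the primary safety objective. None of the 11 listed events uses a low blood count, while a count is already scheduled and baseline values are already required. Haematological toxicity is captured only through general, non-prespecified adverse event recording, and an asymptomatic low count is reduced to Minor or Major.

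The amount of under-recording cannot be calculated from the documents, which give neither a true rate nor an ascertainment rate. What can be shown is how much the missing denominator matters: after no cases, the upper limit moves from 2.8% with all 130 assessed to 5.5% with 65 assessed. That rests on the planned 130 patients. At 100 and 150, the ends of the range in Section 2, the fully assessed limit is 3.6% and 2.4%. Reading the blood-count exclusions as related to doxorubicin is a fair inference from where they stand; the protocol does not say so.

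**What to change.** In Section 5.1, add leukopenia, neutropenia and thrombocytopenia to the primary-objective variables. Grade each by CTCAE 4.03, already cited in Section 7.3, directly from the scheduled post-TACE count, whether or not it was reported as an adverse event.

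In Section 6.1, add a shift table from baseline grade to the grade at that count, or to the worst grade where further counts within 30 days exist. Use the number of patients with a count as denominator, state how many had none, and give an exact 95% confidence interval for the proportion whose grade worsened. Say how a count taken after day 30 is handled; listing it separately is enough.

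State the limits in the plan: a single count after the first procedure may miss a nadir, and it says nothing about retreatments.

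The cost is three values at two time points per patient, 3 x 2 x 130 = 780 entries if none is yet in the booklet, and one table. No test or visit is added, which suits a study that Section 8.5 describes as unfunded. The downside is that some low-grade or pre-existing abnormalities will appear in the safety table; the shift layout lets the reader recognise the pre-existing ones.

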The current trend in most Western countries is to treat HCC by deb-TACE versus c-TACE. Deb-TACE has proven to be very effective in terms of local disease control, with a tendency also towards better overall survival rates although this last point has not yet been confirmed (11-15). Regarding the ideal size of the microsphere that should be used in the hepatocarcinoma deb-TACE, there is still no consensus. This is so to the point that in the current clinical guidelines in force there is no specific recommendation in this regard (1,16-18). In the initial safety and pharmacokinetic studies conducted 10 years ago when this technique was born, microspheres between 500 and 700 microns were used (19). However, today in normal clinical practice it is considered that smaller spheres have more intratumoral penetrance. There are groups that use spheres of 300 to 500 microns (13), others that prefer those of 100 to 300 microns (14) and groups that advocate the use of spheres smaller than 100 microns (20). Experimental studies in animals have shown that reducing the size of the microspheres increases their penetration into the tumor, increasing the amount of drug released in the target tissue, thus achieving a more intense tumoricidal effect (21,22). However, ischemia and lesion of hepatic bile radicals is a potential side effect that arises if very small particles are used. A recent Italian multicenter study shows that in QETA with microspheres smaller than 100 microns (M1 DC Beads, BTG, UK) the safety and efficacy of treatment is similar or somewhat better than that published for other microsphere sizes (23). On the other hand, the recommendations and standard of treatment for QETA in liver metastases from colorectal carcinoma clearly advise the use of microspheres from 75 to 100 microns (24).

Three different brands of drug-releasing microspheres are currently approved for use in the European market. DC Beads® (BTG, Farnham, Surrey, UK), HepaspHERE® (Merit Medical) and Tandem® (Celonova). Most of the literature published on “drug eluting beads” has been made using the DC Beads® platform, which currently has the largest market share. The Tandem® microspheres are of more recent commercialization (May 2012) and because of their characteristics they have a number of potential advantages although at the moment clinical studies on this product are not as abundant as on DC Beads.

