## 1 OBJECTIVES OF THE STUDY

### 1.1 Primary Objective

The primary objective is to evaluate the **tolerance and safety** of TACE with TANDEM™ 100 $\mu$  microspheres preloaded with doxorubicin, describing:

- Appearance and intensity of post-embolization syndrome in the 1st week after treatment
- Major adverse events during the 30 days after TACE.
- Minor adverse events during the 30 days after TACE.
- Mortality derived from treatment.

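### Sections 1.1 and 5.1 disagree on the primary safety window, and the named bile-duct variable leaves out injury before day 30 and dilation without symptoms

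*Combined protocol and SAP*

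**What the plan says.** - **Background and justification.** One harm is tied to small bead size: "ischemia and lesion of hepatic bile radicals is a potential side effect that arises if very small particles are used". The same paragraph then cites a multicentre study of beads below 100 microns with safety similar to, or somewhat better than, that of other sizes.
- **Section 1.1 (Primary Objective).** Safety is to be described through post-embolization syndrome in the first week, "Major adverse events during the 30 days after TACE", "Minor adverse events during the 30 days after TACE", and treatment-related mortality. Apart from post-embolization syndrome, no individual complication is named.
- **Section 5.1 (Study Variables).** Under the heading "Variables related to the primary objective" there are two lists. The early list, for events "derived from the procedure during the first 30 days", has ten items. Liver abscess and acute cholecystitis are among them; bile-duct injury is not. The late list, for events "arising from the procedure between the first 30 days and 6 months", has a single item: "Intrahepatic bile duct injury defined by dilation of biliary radicals with cholestatic symptoms".
- **Section 4.2 (Follow-up).** Imaging is scheduled as "Dynamic liver CT or MRI every 3 m for the first 6 months and then twice a year according to usual practice". A clinical and laboratory visit, including bilirubin and transaminases, takes place 10 to 20 days after discharge.
- **Sections 7.1 to 7.3.** Any unfavorable sign may be an adverse event. All adverse events are to be documented at every visit and classed as minor or major.

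**The concern.** Two things do not fit together.

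First, Section 1.1 closes the adverse-event window at 30 days, while Section 5.1 places an event that can only be counted after day 30 among the primary-objective variables. On one reading, late bile-duct injury is part of the primary safety result; on the other, it is outside it. Section 6.1 does not say which will be reported.

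Second, the named variable is narrower than the hazard described in the Background. It has a lower time limit at day 30, and it needs both dilation and cholestatic symptoms. The scheduled scans are the natural means of detecting dilation without symptoms, yet such a finding does not meet the definition.

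At stake is how a low or zero biliary count would be read. It could be taken as evidence that 100-micron beads spare the ducts, when it would speak only to symptomatic injury after day 30.

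**Working it through.** **1. The plan's own precision figure.** Sections 3.4 and 6.2 state 1.71% for an event proportion of 1.00%, 130 patients and a two-sided 95% asymptotic interval. Half-width = 1.96 × √(0.01 × 0.99 / 130) = 1.71%. It reproduces. It describes sampling error only and does not depend on which cases the definition admits, so it does not settle this point.

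**2. Where each kind of bile-duct injury goes.**

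| Case | 30-day adverse events (1.1) | Early list (5.1) | Late bile-duct variable (5.1) | General record (7.1–7.2) |
|---|---|---|---|---|
| Before day 30, with symptoms | Yes, as an unnamed major or minor event | No item | No, before the window | Yes |
| Before day 30, no symptoms | Only if detected and recorded | No item | No, on both counts | If detected and recorded |
| Day 30 to 6 months, with symptoms | No, after the window | No | **Yes** | Yes |
| Day 30 to 6 months, no symptoms | No, after the window | No | No, symptoms required | If detected and recorded |

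Only one row of four enters the named variable, and that row is outside the 30-day window of Section 1.1.

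**3. When silent dilation would be seen.** The first scheduled scan is at about 3 months. In the normal course, symptom-free dilation is therefore found after the 30-day window has closed. Section 5.1 introduces the imaging under the secondary objectives and has it evaluated by RECIST 1.1; it prescribes no biliary reading. Whether silent dilation is noted thus depends on each center.

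**4. Direction and size.** Let t be the true rate of procedure-related bile-duct injury through 6 months and s the share of cases that the definition excludes. The expected named rate is t × (1 − s). Since s cannot be negative, the named rate cannot exceed t. The documents give neither t nor s, so the shortfall cannot be computed. The values below are assumptions that show the range; they are not estimates.

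| Assumed t | s = 25% | s = 50% | s = 75% |
|---|---|---|---|
| 1% | 0.75% | 0.50% | 0.25% |
| 3% | 2.25% | 1.50% | 0.75% |
| 5% | 3.75% | 2.50% | 1.25% |
| 10% | 7.5% | 5.0% | 2.5% |

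The chance of counting no case at all among 130 is (1 − t(1 − s))^130. At an assumed t of 3% it is 0.97^130 = 1.9% when every case is counted. It becomes 5.2%, 14% and 38% when s is 25%, 50% and 75%.

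**5. What a zero would mean.** With 0 of 130, the exact two-sided 95% upper limit is 1 − 0.025^(1/130) = 2.8%. That limit applies to the injury as defined and gives no bound for dilation without symptoms.

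**The case against.** The strongest reply is that the safety data as a whole are wider than this one variable, and much of that reply stands.

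- A reader might infer that bile-duct injury is absent from the primary objective. The documents do not support that. Section 5.1 files it under "Variables related to the primary objective", as the only late event. Section 1.1 does not name liver failure or abscess either, so its silence on bile ducts proves little. What remains is the disagreement between the two windows.
- A reader might infer that injuries before day 30 disappear. They need not. Section 1.1 does not restrict 30-day events to the ten listed items, Section 7.2 requires all adverse events to be documented, and the visit 10 to 20 days after discharge includes bilirubin. Such a case lacks a named row; it is not necessarily missing from the data.
- A reader might infer that an incidental imaging finding may go unrecorded under the rules. Section 7.1 counts an unfavorable sign without requiring symptoms, so new dilation can qualify. The weakness is practical: nobody is asked to look for it, and the minor category in Section 7.3 is worded around tolerability and discomfort, which leaves the place of a symptom-free sign unclear.
- Dilation with clinical cholestasis is a legitimate definition of a clinically manifest event. Reported as such, it is narrow and not in itself biased. It falls short only when read as the rate of all bile-duct injury, which is the hazard the Background describes.

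**Conclusion.** The point holds in a limited form. Sections 1.1 and 5.1 give different windows for the primary safety variables and must be reconciled. The named bile-duct variable omits injury before day 30 and dilation without symptoms; these may reach only general adverse-event reporting. As a measure of all bile-duct injury, the named rate can therefore only err low, assuming that the cases it does count are genuine.

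The size is unknown. It is tempting to put a multiple on the undercount, but any such multiple is simply the reciprocal of an assumed symptomatic share, and the documents supply no such share. The 2.8% upper limit for a zero count assumes that all 130 patients are followed to 6 months.

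This is an inexpensive improvement in definition and reporting. It does not show that the study's safety data as a whole would be wrong.

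**What to change.** 1. Reconcile Section 1.1 with Section 5.1 so that bile-duct injury through 6 months is stated in both as a primary safety variable, alongside the 30-day adverse events.
2. In Section 5.1, remove the day-30 lower limit for this variable, so that it runs from the procedure to 6 months.
3. Add one field to the data collection at the scans already scheduled: new intrahepatic duct dilation, yes or no, and whether it is judged to arise from the procedure. Keeping the attribution avoids counting dilation from other causes.
4. In Section 6.1, state that cases with and without cholestatic symptoms will be reported in separate rows, each with its 95% confidence interval, and show the cases meeting the present definition from day 30 onward, so that this figure remains visible.

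The cost is wording and one extra data field, with no additional imaging, which suits an observational study in routine practice. The downside is a possibly higher reported biliary rate; the separate rows show how much of it has no symptoms.
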